As observed in the TRD program, most TEAEs reported during esketamine treatment, including those that were most common, were mild or moderate in severity, were observed post dose on the day of dosing, and resolved the same day. In the pooled Phase 3 studies (SUI3001/3002), 89.9% of the participants in the esketamine + standard of care (SOC) group (n=227) and 75.6% in the placebo + SOC group (n=225) experienced at least 1 TEAE during the 4-week double-blind phase. The most common TEAEs (reported by $\geq 10\%$ participants) observed more frequently in the esketamine + SOC group versus placebo + SOC group during the double-blind phase were: dizziness (38.3% versus 13.8%), dissociation (33.9% versus 5.8%), nausea (26.9% versus 13.8%), somnolence (20.7% versus 10.2%), dysgeusia (19.8% versus 12.9%), vision blurred (11.9% versus 4.9%), paresthesia (11.5% versus 3.1%), vomiting (11.5% versus 5.3%), blood pressure increased (11.5% versus 4.0%), sedation (10.1% versus 2.2%), and anxiety (10.1% versus 7.6%). Headache was observed in similar proportion of participants in both groups (20.3% vs. 20.4%). A similar pattern of results was observed in the Phase 2 study SUI2001.

Deaths, Serious Adverse Events and Other Significant Adverse Events**Deaths**

Overall, across all completed and ongoing Phase 1, Phase 2, and Phase 3 studies with esketamine in the MDSI and TRD indications, 8 deaths have been reported up to 2 October 2019.

Participants with TRD:

- Completed Phase 2 and 3 TRD studies: There were 4 deaths reported among the 1,708 participants who had received treatment with esketamine + oral AD in the completed Phase 2 and 3 studies in TRD (611 patient-years exposure). The deaths included 2 completed suicides; 1 of which occurred during the follow-up phase of TRD2003 (20 days after last dose of esketamine) and the other occurred during the OP/MA phase of TRD3004 (last esketamine dose 12 days prior to death). Other causes of death in the completed TRD studies were multiple injuries sustained during a road traffic accident during the double-blind phase of TRD3002 and death as a result of acute cardiac and respiratory failure during the OP/MA phase of TRD3004.
- Ongoing Long-term open-label (OL) Extension Study TRD3008: 3 deaths were reported among the 1,140 participants treated with esketamine in the ongoing extension study TRD3008: 1 death due to **PPD** 1 death due to myocardial infarction, and 1 death due to multiple injuries (accidental polytrauma).

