- Participants who do not meet the predefined nonresponse criteria: For ethical reasons, these participants will also be randomized to receive nasal spray treatment with either placebo, esketamine 56 mg, or esketamine 84 mg, however they will not be included in the primary efficacy analysis set (ie, a separate randomization list will be used).

Previous studies have shown onset of efficacy with esketamine within a day, and durability of an antidepressant effect with repeated dosing. Based on the completed phase 2 and 3 studies, the treatment duration of 4 weeks was selected to demonstrate the treatment effect of esketamine (primary endpoint). To demonstrate an early onset of efficacy with esketamine treatment, Day 2 was selected as the key secondary endpoint.

The open label treatment/observation phase was designed to provide an opportunity for TRD patients completing the double-blind treatment phase to receive esketamine nasal spray, an effective treatment for TRD. This phase will have a recommended dosing frequency that allows for induction and stabilization of treatment with esketamine nasal spray. Participants not willing to receive esketamine can also enter this phase to be observed only, while receiving standard-of-care treatment for depression. A 3-month duration is provided to help participants receiving esketamine transition to available long-term care, if appropriate.

For participants entering the follow-up phase, the one-week duration following the last visit of the double-blind or open-label treatment phase will allow sufficient time to assess safety and tolerability after cessation of nasal spray study medication, including potential withdrawal symptoms.

Treatment Groups and Dose Selection

The 3 treatment groups in the double-blind treatment phase are:

- Esketamine nasal spray (56 mg)
- Esketamine nasal spray (84 mg)
- Placebo nasal spray

The treatment groups will allow for an evaluation of the efficacy, safety, and tolerability of 2 fixed doses of esketamine nasal spray as compared with placebo nasal spray in participants with TRD.

Study Drug

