8.3. Adverse Events, Serious Adverse Events, and Other Safety Reporting

Timely, accurate, and complete reporting and analysis of safety information from clinical studies are crucial for the protection of participants, investigators, and the sponsor, and are mandated by regulatory agencies worldwide. The sponsor has established Standard Operating Procedures in conformity with regulatory requirements worldwide to ensure appropriate reporting of safety information; all clinical studies conducted by the sponsor or its affiliates will be conducted in accordance with those procedures.

Adverse events will be reported by the participant (or, when appropriate, by a caregiver, surrogate, or the participant's representative) for the duration of the study.

For further details on adverse events and serious adverse events (Definitions and Classifications; Attribution Definitions; Severity Criteria; Special Reporting Situations; Procedures) as well as product quality complaints, refer to Section 10.4, Appendix 4, Adverse Events: Definitions and Procedures for Recording, Evaluating, Follow-Up, and Reporting.

8.3.1. Time Period and Frequency for Collecting Adverse Event and Serious Adverse Event Information

All Adverse Events

All adverse events and special reporting situations, whether serious or nonserious, will be reported from the time a signed and dated ICF is obtained until completion of the participant's last study-related procedure, which may include contact for follow-up of safety. Serious adverse events, including those spontaneously reported to the investigator within 30 days after the last dose of study intervention, must be reported using the Serious Adverse Event Form. The sponsor will evaluate any safety information that is spontaneously reported by an investigator beyond the time frame specified in the protocol.

Serious Adverse Events

All serious adverse events occurring during the study must be reported to the appropriate sponsor contact person by study-site personnel within 24 hours of their knowledge of the event.

Information regarding serious adverse events will be transmitted to the sponsor using the Serious Adverse Event Form and Safety Report Form of the CRF, which must be completed and reviewed by a physician from the study site, and transmitted to the sponsor within 24 hours. The initial and

follow-up reports of a serious adverse event should be transmitted electronically or by facsimile (fax).

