- Hospitalizations not intended to treat an acute illness or adverse event (eg, social reasons such as pending placement in long-term care facility)
- Surgery or procedure planned before entry into the study (must be documented in the CRF). Note: Hospitalizations that were planned before the signing of the ICF, and where the underlying condition for which the hospitalization was planned has not worsened, will not be considered serious adverse events. Any adverse event that results in a prolongation of the originally planned hospitalization is to be reported as a new serious adverse event.

The cause of death of a participant in a study within 30 days of the last dose of study intervention, whether or not the event is expected or associated with the study intervention, is considered a serious adverse event.

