5.1.3. Analysis Phases

Double-blind Phase

The analysis reference start date of the double-blind analysis phase is the date of the first dose of double-blind study intervention. The analysis reference end date of the double-blind analysis phase is the maximum of the date of the last visit in the double-blind phase and date of early withdrawal

a. If assessment was performed as part of Visit 2.10 (on the same day) in double-blind phase, duplicate predose assessment is not required.

b. Endpoint (OBS) is only derived for CGI-S.

from the double-blind phase. For participants who entered the open-label phase and received first dose of open-label treatment after the date of last visit in double-blind phase, the analysis reference end date of the double-blind analysis phase is the date of first open-label treatment. For randomized participants who did not receive any study intervention in the double-blind phase, both analysis reference start and end dates are missing for the double-blind analysis phase.

Open-label treatment or Observation Phase

Start and end dates for the open-label treatment or observation phase are only defined for participants who participated in the open-label treatment or observation phase. The analysis reference start date of the open-label treatment or observation phase is the reference end date of the double-blind analysis phase. The analysis reference end date of the open-label treatment or observation phase is the maximum of the date of the last visit in the open-label treatment or observation phase and date of early withdrawal from the open-label treatment or observation phase. For randomized participants who did not participate in the open-label treatment or observation phase, both analysis reference start and end dates are missing for the open-label treatment or observation phase.

Follow-up Phase

Start and end dates for the follow-up phase are only defined for participants who continued into the follow-up phase. The analysis reference start date of the follow-up analysis phase is the day after the reference end date for the double-blind analysis phase (for participants who did not continue into open-label treatment or observation phase), or the open-label treatment or observation phase (for participants who participated in the open-label treatment or observation phase). The analysis reference end date of the follow-up analysis phase is the maximum of the last follow-up visit date or the disposition date at follow-up.

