- For participants who discontinued double-blind treatment but continued to be assessed until the end of double-blind phase (Day 28), AEs will be considered as treatment-emergent for the double-blind phase only if they satisfy the condition: double-blind phase start date /time ≤ AE onset date/time ≤ last day of double-blind treatment.

Open-label treatment phase:

- For participants who received open-label esketamine nasal spray, all AEs that are assigned to the open-label treatment phase will be considered as treatment-emergent if they satisfy the condition: open label treatment phase start date/time≤ AE onset date/time ≤ open label treatment phase end date.
 - AEs that occur on the last day of double-blind phase but AE onset time is after open-label dosing will be considered as treatment-emergent for the open-label treatment phase.

Observation phase:

• For participants who received SOC only in the observation phase, all AEs that are assigned to the observation phase will not be considered as treatment-emergent if they satisfy the condition: double-blind phase end date+1≤ AE onset date ≤ observation phase end date.

Follow-up phase:

• Any AEs that are assigned to the follow-up phase will not be considered as treatmentemergent. AEs during the follow-up phase should satisfy the condition: follow-up phase start date ≤AE onset date ≤follow-up phase end date.

Summary tables will be provided for adverse events by phase:

- AEs
- Serious AEs (SAEs)
- AEs leading to discontinuation of each study agent within a study intervention
- AEs by severity
- AEs by relationship to each study agent within a study intervention
- AEs of special interest

In addition to the summary tables, listings will be provided for participants who had:

- SAEs
- AEs leading to discontinuation of study intervention
- AEs of special interest

Incidence of other treatment-emergent adverse events of special interest will be summarized. See Appendix 7 for list of adverse events in each category.

The proportion of TEAEs occurring on dosing days and the proportion of TEAEs that occur on dosing days with same day resolution will be summarized. Duration and resolution time of severe TEAEs will also be summarized.

A listing of participants who died will be provided.

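### SAEs and deaths reported after the follow-up phase ends but within 30 days of last dose fall in no by-phase SAE summary table

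*SAP*

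**What the plan says.** **Reporting window.** Protocol 8.3.1 runs general adverse event reporting from consent "until completion of the participant's last study-related procedure, which may include contact for follow-up of safety". For serious events it goes further: those "including those spontaneously reported to the investigator within 30 days after the last dose of study intervention, must be reported" on the SAE form. Protocol 10.4.5 adds deaths: "The cause of death of a participant in a study within 30 days of the last dose of study intervention" counts as a serious adverse event, whether or not it is expected or associated with study drug.

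**Length of follow-up.** Protocol 4.2 describes "the one-week duration following the last visit of the double-blind or open-label treatment phase". The Schedule of Activities has one follow-up visit, about a week after the last visit, and no contact at 30 days.

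**Analysis phase.** SAP 5.1.3 defines follow-up dates only for participants who continued into that phase. The "end date of the follow-up analysis phase is the maximum of the last follow-up visit date or the disposition date at follow-up".

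**Assignment and tables.** SAP 5.6.2 states "AEs during the follow-up phase should satisfy the condition: follow-up phase start date" on or before AE onset, with onset no later than the phase end date. The summary tables for AEs, SAEs, severity, relationship and special-interest events are all by phase. The section also plans listings of participants with SAEs, of participants with special-interest events and of participants who died, without restricting them to a phase. Protocol 9.4.5 promises narratives for deaths and SAEs.

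**The concern.** The reporting window is tied to the last dose, whereas the analysis window is tied to the follow-up visit. Where the visit comes well before last dose + 30 days, a serious event can be reported as the protocol requires and still satisfy no phase rule. The SAP has no residual or post-study category, and its Appendix 2 declares no change from the protocol-planned analyses.

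Participants who never entered follow-up have no follow-up dates at all, so any serious event reported after their last phase ended is also unassigned.

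At stake are the SAE counts by treatment group. Suicidal ideation and behavior is a stated safety objective, and suicidality is a special-interest category. A serious event of that kind could appear in a listing and a narrative while the SAE table beside them does not count it.

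**Working it through.** The plan gives no figure of its own to reproduce beyond the 30-day window, so the check is day arithmetic.

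**Inputs**
- Reporting window: last dose + 30 days (Protocol 8.3.1, 10.4.5).
- Dosing and visit days: Schedule of Activities. The last scheduled double-blind dose is Day 25 and the last double-blind visit Day 28. The last open-label visit, which can be a dosing visit, is Day 105. Every-other-week dosing is allowed in Weeks 13 to 16, so a completer's last dose may be earlier.
- Follow-up visit: taken as 7 days after the last phase visit, so Day 28 + 7 = Day 35 or Day 105 + 7 = Day 112.
- Assumption: the follow-up disposition date equals the visit date. A later disposition date shortens the gap day for day.

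**Formula**

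Uncovered days = max(0, last dose day + 30 − follow-up day)

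| Path | Last dose | Window closes | Follow-up | Uncovered days |
|---|---|---|---|---|
| Double-blind completer, does not continue | 25 | 55 | 35 | 20 (Days 36–55) |
| Open-label completer | 105 | 135 | 112 | 23 (Days 113–135) |
| Open-label completer | 98 | 128 | 112 | 16 |
| Open-label completer | 91 | 121 | 112 | 9 |
| Drug stopped after Day 8, visits kept to Day 28 | 8 | 38 | 35 | 3 |
| Drug stopped after Day 4, visits kept | 4 | 34 | 35 | 0 |
| Drug stopped after Day 1, visits kept | 1 | 31 | 35 | 0 |
| Left the phase after Day 1, early withdrawal visit Day 8 | 1 | 31 | 15 | 16 |
| Observation only after double-blind | 25 | 55 | 112 | 0 |

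As a share of the 30-day window, the largest two cases are 20/30 = 67% and 23/30 = 77%. Observation-only participants have no gap because their window closes on Day 55, inside an observation phase that runs to Day 105.

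**Which outputs change.** SAP 5.6.2 never treats a follow-up event as treatment-emergent. Extending follow-up therefore leaves the double-blind and open-label treatment-emergent tables as they are. Only the follow-up AE and SAE tables could gain events.

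**After the fix.** With the phase end set to the later of its current value and last dose + 30 days, uncovered days are 0 on every path. The extension is 20 days for the double-blind completer, up to 23 for the open-label completer and 0 for observation-only participants.

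**The case against.** The strongest reply is that tabulating the actively followed period, and listing and narrating later passive reports, is a defensible choice. Several parts of it stand.

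- **Reporting is passive.** A reader might infer that the protocol actively collects serious events to 30 days. It does not: the clause covers spontaneous reports, and nothing is scheduled at that point. Few events may arise, and the documents give no rate for the interval.
- **Nothing vanishes.** A reader might infer that late events drop out of reporting. They do not, because the listings and narratives carry no phase limit.
- **The gap is not universal.** The 67% and 77% shares belong to two particular paths. Some paths have no gap, and a late disposition date can extend the phase.
- **Participants without a follow-up phase.** All dosed participants are meant to attend follow-up. After consent withdrawal no further assessments are allowed, and lost participants cannot be reached, so little would be left to assign.
- **The precedents prove less than they seem to.** Protocol 2.2 reports a suicide 20 days and a serious cerebrovascular accident 25 days after last dose, but both fell within follow-up phases. They show that serious events can occur at such intervals, not that a phase rule left one out.

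What the reply does not supply is a rule. The SAP does not say that late SAEs are deliberately left to listings. Its definitions simply leave them unassigned, and listings and narratives do not give incidence by treatment group.

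**Conclusion.** The mismatch is real and limited to one kind of output. SAEs and deaths with onset after the follow-up analysis end date but within 30 days of last dose are reportable under the protocol and enter no by-phase SAE summary under the SAP. The uncovered interval runs from 0 to 23 days depending on the path, assuming a follow-up visit 7 days after the last phase visit and disposition on the same date. How many events this affects cannot be estimated from the documents.

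The documents do not support reading this as a threat to the efficacy inference or as understated treatment-emergent rates. It is worth correcting because SAE tables and SAE listings in one report should agree, and the correction is cheap.

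**What to change.** In SAP 5.1.3, add an end date used only for SAEs and deaths: the later of the current follow-up end date and last nasal spray dose + 30 days. Define it for every dosed participant who has left the double-blind and open-label or observation phases, whether or not the follow-up visit took place. Apply it in SAP 5.6.2 to SAEs and deaths, including serious suicidality events. An equivalent alternative is a separate post-study row in the SAE tables.

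Do not extend it to all special-interest suicidality events. Non-serious events are not collected after the last study-related procedure, so those counts would be incomplete by construction.

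Add a footnote that events after the follow-up visit come from spontaneous reports.

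The cost is a few lines of SAP text and one derivation, with no new data. The downside is that the late counts are passively ascertained and may be incomplete, which the footnote discloses.

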5.1.4. Imputation of Efficacy

Imputation method for missing data will include the following methods (Table 5).

Table 5: Imputation of Missing Efficacy Data

Imputation	Text
Multiple Imputation (MI) method	Delta Adjustment

Imputation of total scores will be performed for the following efficacy scales as shown in Table 6 below. If the number of items with missing scores is greater than the maximum number of items presented in the table, the total score will be missing.

For the remaining efficacy assessments which require adding multiple item scores, the total score will be missing if any item score is missing.

Table 6: Imputation of Total Score for Efficacy Scales

	Total Number	Maximum Number of Items That Can Be	
Efficacy Scale	of Items	Missing *	Formula for Total Score
MADRS	10	1	Sum of non-missing item scores *

	(10 / number of non-missing items)

5.2. Participant Disposition

The number of participants in the following disposition categories will be summarized throughout the study by intervention group and overall for the all randomized full efficacy, responder, safety, observation and open-label analysis sets as appropriate for the relevant phases:

- Participants randomized
- Participants who received study intervention during each phase
- Participants who completed and discontinued and reasons for discontinuation of study intervention during each phase
- Participants who completed, terminated and reasons for termination from each phase of the study

Listings of participants will be provided for the following categories:

- Participants who discontinued double-blind study intervention
- Participants who discontinued double-blind phase
- Participants who discontinued open-label study intervention
- Participants who discontinued open-label phase
- Participants who terminated study prematurely (trial disposition page)
- Participants who were unblinded during the study period
- Participants who were randomized yet did not receive study intervention.

5.3. Primary Endpoint Analysis

The multiplicity, with regard to testing multiple endpoints (the primary [Day 28] and the key secondary [Day 2]) and multiple doses (esketamine 84 mg vs placebo and esketamine 56 mg vs placebo), will be controlled by a sequential gatekeeping method using the Hochberg procedure, a familywise error rate of 0.05 and a truncation parameter of 1. For the primary hypothesis (Day 28), if the largest p-value of the two dose comparisons of esketamine 84 mg vs placebo and esketamine 56 mg vs placebo is less than two-sided 0.05 level, both esketamine 56 mg and esketamine 84 mg will be declared statistically significantly different from placebo. If the largest p-value of primary endpoint tests is greater than or equal to 0.05, the comparison associated with this p-value will be declared not statistically significant and the smaller p-value will be compared to the 0.025 level. The key secondary hypothesis (Day 2) will be tested using the Hochberg procedure only if the null hypothesis for the primary endpoint is rejected for both doses.

